6 DRUGS AND DOSING (OR TREATMENT PROCEDURES)

6.1 DRUG DOSAGE, ADMINISTRATION AND SCHEDULE

The UT-15C tablets are sustained release osmotic tablets. UT-15C tablets are provided as 0.125, 0.25, 0.5, 1.0, and 2.5 mg tablet strengths. The 0.125, 0.25, 0.5, 1.0, and 2.5 mg tablets are colored blue, green, white, yellow, and pink, respectively. The formulation contains pharmaceutically acceptable excipients used in other approved drug products.

For subjects who were randomly allocated to receive placebo in TDE-PH-310, dosing of UT-15C will be initiated and optimized as in the previous protocol, including all safety monitoring and periodic telephone contacts. That is, the first dose of UT-15C (0.125 mg) should be taken by the subject at the site immediately after (approximately 10 minutes) consuming food. Oral dosing of study drug will be continued at 0.125 mg TID (every 6 to 8 hours) immediately after (approximately 10 minutes) consuming food. Subjects must be instructed to take the appropriate amount of UT-15C tablets based upon their prescribed dose. For the first 4 weeks, each dose of study drug should be adjusted in 0.125 mg increments no

more than every 24 hours as clinically indicated. Following 4 weeks of treatment, each dose of study drug may be adjusted in 0.125 or 0.25 mg increments every 24 hours as clinically indicated. Doses of UT-15C should continue to be increased in the absence of dose-limiting drug-related adverse effects, to ensure the subject receives the optimal clinical dose throughout the study. There is no maximum dose of UT-15C in this open-label study.

Subjects who were randomly allocated to receive UT-15C in TDE-PH-310 will begin the open-label study at the same dose they were receiving at the Study Termination Visit in TDE-PH-310, and subsequent adjustments will be made based on symptoms of PAH and adverse effects.

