5 SEQUENCE OF PLANNED ANALYSES

Along with the safety information from the parent study (TDE-PH-310), safety information from the TDE-PH-311 study will be provided to the Data Monitoring Committee (DMC) periodically for safety review.

At the time of study completion and unblinding for the parent study (TDE-PH-310), a data cut for the TDE-PH-311 study will be performed to facilitate the analysis for the TDE-PH-311 study. Analyses based on additional data cuts and the final analyses at the time of study closing will be performed separately.

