8 GENERAL CONSIDERATIONS FOR DATA ANALYSES

All data included in each data cut will be listed. In general, listings will be sorted by subject number and scheduled assessment (if applicable) or the visit date. Listings will include assessment date, assessment time (if available), and study day. The study day is calculated as the assessment date minus the date of the first UT-15C dose in the TDE-PH-311 study. For data collected on a fixed schedule, the assessment identifier will also be included on the listing.

In general, the data will be summarized by visit window. The visit window is calculated based on the time from the first dosing date of UT-15C in the TDE-PH-311 study. For all presentations of the summary tables, the data will be presented by subjects in the UT-15C and placebo groups from the parent study (TDE-PH-310) and overall.

For continuous variables, the summary statistics will include the mean, standard deviation, median, minimum, and maximum. Minimums and maximums will be expressed using the level of precision in which the variable was collected. All other statistics will be rounded, using an additional decimal point. For discrete variables, summaries will include the frequency and percent in each category. Percentages will be rounded to 1 decimal point. Whenever practical, categories of discrete variables will be ordered and labeled as they appear in the electronic case report form (eCRF), and all categories represented on the eCRF will be included in summaries, even when they do not apply to any subjects in the study.

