11 SAFETY ANALYSES

11.1 ADVERSE EVENTS

AEs are captured from the time the Informed Consent Form is signed. Any AEs that are ongoing at the Study Termination Visit from study TDE-PH-310 are recorded as continuing AEs in TDE-PH-311 study. All AEs with an onset date on or after the first dose of UT-15C in the TDE-PH-311 study or AEs ongoing from the parent study will be included in data listing and summaries.

The AEs will be coded using the Medical Dictionary for Regulatory Activities (MedDRA), and all summaries will utilize the Preferred Term (PT) and/or System Organ Class (SOC). All AEs and serious AEs will be organized by treatment group in the parent study, and listed by subject, including onset date (day), cessation date (day), verbatim term, corresponding PT and SOC, seriousness, date AE became serious, severity, frequency, relationship to study drug, action taken with study drug, and outcome.

The overall summary of AEs includes the number of subjects with any AE, the number of subjects with any study drug-related AEs, the number of subjects with AEs leading to study drug withdrawal, the number of subjects with any serious AEs, the number of subjects with any severe AEs, and the number of subjects with any study drug-related severe AEs.

The summaries of AEs by SOC and PT will be provided by treatment group in the parent study and overall. The summaries of AEs, serious AEs, severe AEs, AEs probably or possibly related to UT-15C, serious AEs probably or possibly related to UT-15C, and AEs

leading to permanent discontinuation of UT-15C will include the number of subjects (percent of subjects) and number of events for each reported PT.

The summary of AEs adjusted for UT-15C exposure will include the number of subjects (percent of subjects) and number of events for each reported PT, as well as the number of events per patient-year of exposure.

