12 APPENDICES**12.1 LIST OF TABLES**

Table titles suggested here may be altered or edited as appropriate by the clinical data programmers while maintaining the original intent of the summary.

Table Number	Table Title
14.1.1	Summary of Subject Accountability
14.1.2	Summary of UT-15C Exposure
14.1.3	Summary of UTC Exposure in TDE-PH-310 and TDE-PH-311 Studies
14.1.4	Summary of Demographics
14.1.5	Summary of Baseline Characteristics
14.1.6	Summary of PAH History
14.1.7	Summary of Study Entry Criteria
14.1.7.1	Summary of UT-15C Dosing
14.1.7.2	Summary of UT-15C Dosing by Background PAH Therapy
14.1.8.1	Summary of Concomitant Medications Ongoing from the Previous Study
14.1.8.2	Summary of Concomitant Medications Added in TDE-PH-311 Study
14.2.1.1	Summary of 6MWD (meter) by Visit
14.2.1.2	Summary of Borg Dyspnea Score by Visit
14.2.1.3	Summary of 6MWD (meter) by PAH Etiology
14.2.1.4	Summary of 6MWD (meter) by Baseline WHO Functional Class
14.2.1.5	Summary of 6MWD (meter) by Quartiles of the Last UT-15C Dose
14.2.1.6	Summary of 6MWD Achieving > 440 Meters by Visit
14.2.1.7	Summary of 6MWD Achieving >440 Meters by Baseline 6MWD Category
14.2.1.8	Summary of WHO Functional Class by Visit
14.3.1.1	Overall Summary of Adverse Events
14.3.1.2	Summary of Adverse Events by System Organ Class and Preferred Term
14.3.1.3	Summary of Serious Adverse Events by Preferred Term
14.3.1.4	Summary of Severe Adverse Events by Preferred Term
14.3.1.5	Summary of Serious Adverse Events Probably or Possibly Related to UT-15C by Preferred Term
14.3.1.6	Summary of Adverse Events Probably or Possibly Related to UT-15C by Preferred Term
14.3.1.7	Summary of Adverse Events Leading to Permanent Discontinuation of UT-15C
14.3.1.8	Summary of Disease-Related Events
14.3.1.9	Summary of Adverse Events Adjusted for Length of UT-15C Exposure
14.3.2.1	Listing of Deaths
14.3.2.2	Summary of Deaths
14.3.2.3	Listing of Serious Adverse Events

Table Number	Table Title
14.3.4.1	Summary of Hematology Data
14.3.4.2	Summary of Hematology Shifts from Baseline
14.3.4.3	Summary of Clinical Chemistry Data
14.3.4.4	Summary of Clinical Chemistry Shifts from Baseline
14.3.4.5	Summary of Urinalysis Data
14.3.4.6	Summary of Vital Signs

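### AEs are summarized only as one events-per-patient-year rate over all follow-up, which can drift down between data cuts if AEs cluster early or if carried-over AEs are counted

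*SAP*

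**What the plan says.** SAP 11.1 plans a single exposure-adjusted AE summary. For each preferred term it reports subjects and events, "as well as the number of events per patient-year of exposure". No time interval is given. The list in SAP 12.1 has one matching entry, Table 14.3.1.9, "Summary of Adverse Events Adjusted for Length of UT-15C Exposure", and no AE table by time since first dose.

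Five other provisions bear on how that rate will behave:

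- **Columns.** SAP 8 says that in all summary tables "the data will be presented by subjects in the UT-15C and placebo groups from the parent study (TDE-PH-310) and overall".
- **Numerator.** SAP 11.1 takes AEs with onset on or after the first TDE-PH-311 dose, and adds that "AEs ongoing from the parent study will be included in data listing and summaries". No exception is made for the rate table.
- **Denominator.** SAP 9.1 summarizes both TDE-PH-311 exposure and, for former UT-15C subjects, exposure combined with the parent study. SAP 11.1 does not say which one divides the events.
- **Dosing.** Under Protocol 6.1, for former placebo subjects "dosing of UT-15C will be initiated and optimized as in the previous protocol", while former UT-15C subjects "will begin the open-label study at the same dose they were receiving at the Study Termination Visit in TDE-PH-310".
- **Timing.** SAP 5 plans a first cut when the parent study is unblinded, after which "Analyses based on additional data cuts and the final analyses at the time of study closing will be performed separately". Protocol 3.6 expects the study to last about 6 years.

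Protocol 10.3 says that safety as well as efficacy data will be examined for trends over time.

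**The concern.** Total events divided by total patient-years describes the risk at any given time only if the event rate is constant. If it is not, the figure is an average whose value depends on how long subjects have been followed. Later cuts of a study of about 6 years then give different figures from earlier ones even if risk at each point after first dose is unchanged. A reader comparing cuts could take the difference for improving tolerability.

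Long-term safety is the first-listed secondary objective. Walk distance, Borg score, functional class, laboratory values, vital signs and dose are all summarized by visit. AEs are not, so the SAP leaves the protocol's commitment on time trends unmet for this endpoint. That gap does not depend on any assumed rate.

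**Working it through.** The documents give no AE rate by time since first dose, so there is no planned figure to reproduce. All rates below are assumptions.

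**1. Early clustering**

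Inputs: an early period of w = 12 weeks, the period of at least weekly calls about AEs and titration in Protocol 6.1, so w = 12/52.18 = 0.230 years; mean follow-up T; rates r₁ in the early period and r₂ afterwards; no dropout.

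Pooled rate = [r₁w + r₂(T − w)] / T = r₂ + (r₁ − r₂)w/T

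- 20 then 4 per patient-year: 4 + 16 × 0.230/T = 4 + 3.68/T
- 10 then 4 per patient-year: 4 + 6 × 0.230/T = 4 + 1.38/T

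For the overall column, assume half the subjects are former placebo, all have equal follow-up, and former UT-15C subjects stay at 4 throughout. The excess is then halved: 4 + 1.84/T and 4 + 0.69/T.

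| Column (assumed rates) | T = 1 y | T = 3 y | Fall |
|---|---|---|---|
| Former placebo (20/4) | 7.68 | 5.23 | 32% |
| Overall, 50/50 (20/4) | 5.84 | 4.61 | 21% |
| Former placebo (10/4) | 5.38 | 4.46 | 17% |
| Overall, 50/50 (10/4) | 4.69 | 4.23 | 10% |
| Former UT-15C (constant 4) | 4.00 | 4.00 | 0% |

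Sensitivity to the early/late ratio, with the late rate set to 1 and T going from 1 to 6 years:

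- ratio 0.5: 0.89 to 0.98 (a rise)
- ratio 1: 1.00 throughout
- ratio 2: 1.23 to 1.04 (16% fall)
- ratio 3: 1.46 to 1.08 (26% fall)
- ratio 5: 1.92 to 1.15 (40% fall)

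With an assumed discontinuation hazard of 0.2 per year, the last three falls become 15%, 25% and 37%.

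**2. Carried-over AEs**

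Let k be the number of AEs per subject already ongoing at entry (not given in the documents; 0.5 to 2 assumed) and λ a constant new-onset rate.

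Pooled rate = (k + λT)/T = λ + k/T

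| λ per patient-year | k | T = 1 y | T = 6 y | Fall |
|---|---|---|---|---|
| 1 | 0.5 | 1.50 | 1.08 | 28% |
| 1 | 1 | 2.00 | 1.17 | 42% |
| 1 | 2 | 3.00 | 1.33 | 56% |
| 3 | 1 | 4.00 | 3.17 | 21% |

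Here the true rate never changes. The fall comes only from spreading a fixed count over more exposure, and it affects any column with k above 0.

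**3. What an interval split does**

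With events and exposure both cut at Week 12, each interval returns r₁ or r₂ whatever the value of T. This works only if carried-over AEs are left out. At k = 1, assigning them to Weeks 0 to 12 would add 1/0.230 = 4.35 per patient-year to that interval and create an early excess where none exists.

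**The case against.** A reader might infer that the rate must fall simply because follow-up lengthens. The documents do not support that: at a constant new-onset rate with no carried-over AEs it does not move. They make an early excess plausible. New starters titrate, the synopsis warns that sudden dose changes may bring intolerable effects, and in the 16-week TDE-PH-301 study 14% on UT-15C against 5% on placebo discontinued for AEs. None of this is a rate by time since first dose.

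A reader might also infer that new starters' early burden is hidden among continuing subjects, or that a 32% fall applies to everyone. The parent-arm columns largely answer both. Mixing over time remains within the former placebo column and in the overall column, and the 32% belongs to the former placebo column alone under the steeper assumption.

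Nor is there a documented boundary between titration and maintenance. Protocol 6.1 says "Doses of UT-15C should continue to be increased in the absence of dose-limiting drug-related adverse effects", with no maximum dose. Intervals can be defined by time since first dose, but not by treatment phase.

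Finally, no hypothesis test is planned, counts and percentages stand beside the rate, onset day is listed, and SAP 1 allows additional analyses. This limits the harm, since the interval rates could be recovered later. It does not put them in the plan, and it does not remove carried-over AEs from the numerator.

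**Conclusion.** The point holds in conditional form, as a worthwhile but minor improvement. What the documents establish is that the only planned AE rate is pooled over all follow-up, that nothing splits AEs by time since first dose despite Protocol 10.3, that carried-over AEs are in the summaries, and that the denominator is not named.

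The size of any drift is not established. Under the assumed patterns, the fall from 1 to 3 years is 17% to 32% in the former placebo column, 10% to 21% overall, and nil at a constant rate. The carried-over effect needs no early excess. It does need the SAP's general inclusion rule to apply to Table 14.3.1.9, and its size depends on the unknown number of ongoing AEs per subject.

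**What to change.** In Table 14.3.1.9, for each preferred term, by parent arm and overall:

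- Add new-onset events (onset on or after the first TDE-PH-311 dose) and TDE-PH-311 patient-years for Weeks 0 to 12, >12 to 48 and >48 since that dose, each interval with its own denominator.
- Show AEs ongoing from TDE-PH-310 as a separate count and exclude them from every rate, including the pooled one.
- State in SAP 11.1 that the denominator is TDE-PH-311 exposure, which matches a numerator of events arising in that study.
- Keep the pooled column.

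The cut points are a choice. Week 12 is where weekly calls end, and Week 48 is an existing visit. No new data are needed. The cost is a wider table with sparse counts for rare terms.

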11.2 DISEASE-RELATED EVENTS

Disease-related events will be listed by the subject number, treatment group in parent study, and events (yes/no). The summary will include the number (percent) of subjects who reported each symptom by treatment group in the parent study and overall. Disease-related events include abdominal pain, anorexia, ascites, chest pain, cool extremities, cor pulmonale, cough, cyanosis, dizziness, dyspnea, general edema, hemoptysis, fatigue, hypoxia, loss of consciousness, nausea, orthopnea, pallor, palpitations/cardiac arrhythmia, paroxysmal nocturnal dyspnea, pulmonary hypertension exacerbation, syncope, tachycardia, weight loss/gain, vasovagal reaction, and vomiting.

11.3 DEATHS

All deaths will be listed (including those occurring within 30 days of the last UT-15C dose) by subject, and will include the subject number, treatment group in the parent study, date of assessment (day), whether subject died, date of death (day), and cause of death (including other, specify text [if applicable]). An additional listing of deaths will include the subject number, first UT-15C dose in TDE-PH-311 study, last UT-15C dose (day) in TDE-PH-311 study, date of death (day), and cause of death. The summary of deaths will be presented by the parent study and overall and will include the number (percent) of subjects who died (including those within 30 days of study participation) and their causes of death.

Time to death will be calculated as:

(the death date – the date of the first UT-15C dosing in TDE-PH-311 study)

The Kaplan-Meier (K-M) estimator will be provided for the time to death, and K-M plots will be provided by treatment group in the parent study.

11.4 CLINICAL LABORATORY TESTS

Laboratory results will be mapped into the analysis visit based on the assessment date. The laboratory data will be listed by subject and treatment group in the parent study, including all hematology and clinical chemistry parameters by analysis visit. The listings will include the collection date/times (day), laboratory test, and results. The normal laboratory reference ranges will be included in the listings. A designation for low (L) or high (H) will be included for those laboratory values that are outside the relevant normal range. The listing of urinalysis will also be presented by subject and the treatment group in the parent study, and will include each scheduled and unscheduled urinalysis assessment. The laboratory sample collection date/time (day), laboratory test, normal range, designation for high or low, and analysis visit will be provided for each assessment, as well as the result of the test.

For hematology and clinical chemistry parameters, the original values and their changes from Baseline (defined as the last measurement prior to the first dose of UT-15C in the TDE-PH-311 study) will be summarized for each analysis visit by the treatment group in the parent study and overall. Shift tables will also be provided. For urinalysis results, the number and percent of subjects within each category will be summarized for all analysis visits by treatment group in the parent study and overall.

Pregnancy test results for the female subjects will be organized by treatment group in the parent study, and listed by subject number, analysis visit, and did the subject become pregnant during the study (yes/no).

11.5 VITAL SIGNS

Vital sign results will be mapped into the analysis visit based on the assessment date. The vital sign data will be listed by subject and treatment group in the parent study for each analysis visit by assessment date/time (day), weight, heart rate, blood pressure, and respiration rate. The original measures and their changes from Baseline (defined as the last measurement prior to the first UT-15C dosing in the TDE-PH-311 study), and descriptive statistics, will be summarized for all analysis visits by the treatment group in the parent study and overall.

12 APPENDICES**12.1 LIST OF TABLES**

Table titles suggested here may be altered or edited as appropriate by the clinical data programmers while maintaining the original intent of the summary.

Table Number	Table Title
14.1.1	Summary of Subject Accountability
14.1.2	Summary of UT-15C Exposure
14.1.3	Summary of UTC Exposure in TDE-PH-310 and TDE-PH-311 Studies
14.1.4	Summary of Demographics
14.1.5	Summary of Baseline Characteristics
14.1.6	Summary of PAH History
14.1.7	Summary of Study Entry Criteria
14.1.7.1	Summary of UT-15C Dosing
14.1.7.2	Summary of UT-15C Dosing by Background PAH Therapy
14.1.8.1	Summary of Concomitant Medications Ongoing from the Previous Study
14.1.8.2	Summary of Concomitant Medications Added in TDE-PH-311 Study
14.2.1.1	Summary of 6MWD (meter) by Visit
14.2.1.2	Summary of Borg Dyspnea Score by Visit
14.2.1.3	Summary of 6MWD (meter) by PAH Etiology
14.2.1.4	Summary of 6MWD (meter) by Baseline WHO Functional Class
14.2.1.5	Summary of 6MWD (meter) by Quartiles of the Last UT-15C Dose
14.2.1.6	Summary of 6MWD Achieving > 440 Meters by Visit
14.2.1.7	Summary of 6MWD Achieving >440 Meters by Baseline 6MWD Category
14.2.1.8	Summary of WHO Functional Class by Visit
14.3.1.1	Overall Summary of Adverse Events
14.3.1.2	Summary of Adverse Events by System Organ Class and Preferred Term
14.3.1.3	Summary of Serious Adverse Events by Preferred Term
14.3.1.4	Summary of Severe Adverse Events by Preferred Term
14.3.1.5	Summary of Serious Adverse Events Probably or Possibly Related to UT-15C by Preferred Term
14.3.1.6	Summary of Adverse Events Probably or Possibly Related to UT-15C by Preferred Term
14.3.1.7	Summary of Adverse Events Leading to Permanent Discontinuation of UT-15C
14.3.1.8	Summary of Disease-Related Events
14.3.1.9	Summary of Adverse Events Adjusted for Length of UT-15C Exposure
14.3.2.1	Listing of Deaths
14.3.2.2	Summary of Deaths
14.3.2.3	Listing of Serious Adverse Events

Table Number	Table Title
14.3.4.1	Summary of Hematology Data
14.3.4.2	Summary of Hematology Shifts from Baseline
14.3.4.3	Summary of Clinical Chemistry Data
14.3.4.4	Summary of Clinical Chemistry Shifts from Baseline
14.3.4.5	Summary of Urinalysis Data
14.3.4.6	Summary of Vital Signs

12.2 LIST OF LISTINGS

Listing titles suggested here may be altered or edited as appropriate by the clinical data programmers while maintaining the original intent of the listing.

Appendix Number	Listing Title
16.2.1	Subject Disposition and Study Drug Exposure
16.2.2.1	Entry Criteria
16.2.2.2	Protocol Deviations
16.2.4.1	Demographics
16.2.4.2	PAH History
16.2.4.3	Concomitant Medications
16.2.5	UT-15C Dose
16.2.6.1	6-Minute Walk Test and Borg Dyspnea Score Data
16.2.6.2	WHO Functional Class for PAH
16.2.6.3	Death Records
16.2.6.4	Disease-Related Events
16.2.7	Adverse Events
16.2.8.1	Laboratory Results – Clinical Chemistry
16.2.8.2	Laboratory Results – Hematology
16.2.8.3	Laboratory Results – Urinalysis
16.2.8.4	Pregnancy Test Results (Female Subjects Only)
16.2.8.5	Vital Signs

12.3 LIST OF FIGURES

Figure titles suggested here may be altered or edited as appropriate by the clinical data programmers while maintaining the original intent of the figure.

Figure Number	Figure Title
14.2.1	Kaplan-Meier Plot of Time to Death by Treatment Group in Parent Study
